The study will enroll patients of either gender aged from 6 months to 6 years old who are admitted to hospital within 48 hours of the onset of acute intestinal infection (AII), presumably of viral etiology. The children with typical viral gastroenteritis/enteritis symptoms will be enrolled in the screening. The key symptom is acute watery diarrhea without visible pathological impurities (transparent mucus is possible) at least 3 times a day. Virus detection in stool specimens will be performed by polymerase chain reaction (PCR). After the parent/adopter signs a parents/adopters information sheet (Informed Consent form) for the child's participation in the clinical trial, the recording of medical history data, a medical examination including the evaluation of symptoms on the Clinical Dehydration Scale (CDS) by pediatrician, and laboratory examination⁵ will be performed during Visit 1 (Day 1). If inclusion criteria are met and non-inclusion criteria are absent (day 1), the patient will be included in the trial and randomized to administer either Ergoferon or Placebo.

In addition to the standard/pathogenetic therapies, group 1 patients will take Ergoferon following a 5-day regimen, whereas group 2 patients will receive Placebo. The parents/adopters of patient will be provided with patient diary and instructed how to fill it.

Before treatment stool specimens will be collected from the patients for detection and differentiation of Rotavirus A, Norovirus 2 genotype, Astrovirus, Adenovirus F, Shigella spp., enterovasive E.coli (EIEC), Salmonella spp., and thermophilic Campylobacter spp. using a PCR assay⁶ to diagnose the etiology of intestinal infection. In total the patients will be monitored for 10 days (screening, randomization, treatment initiation – Day 1; the treatment on Days 1 - 5; observation in hospital – Day 6, and follow-up period – Day 7 - 10). During the treatment and inpatient observation periods (Days 1-6, Visits 1-6), the patients will be examined daily by

CONFIDENTIAL Page 3 of 14

⁵ If an eligible patient (not meeting the non-inclusion criteria) is enrolled after the collection of blood and urine specimens for laboratory testing (specifically for the current hospitalization), these test results will be considered as the initial variables in the analysis of safety endpoints (i.e., no repeat specimen collection will be required provided the laboratory variables evaluated are those defined by this protocol).

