⁶ The data of a patient whose PCR test indicates a bacterial etiology of acute intestinal infection will not be included in the analysis of treatment efficacy. For the sake of sufficiency of data for the efficacy analysis, it is statistically assumed that 50% of patients will test negative for viral etiology of acute intestinal infection.

pediatrician, and the examination results, including the CDS scores, will be recorded in source documents. The patient's parent/adopter will fill patient diary on a daily basis, recording the presence/absence of diarrhea signs, vomiting, and body temperature. The pediatrician will check correctness of diary filling. After discharge on day $10 \ (\pm 1)$ Visit 7 is scheduled (personal at the site/at home or distant/phone call) to interview the parents/adopters about the patient's health, presence of any complications, and use of medications (the investigator will fill out a questionnaire).

Collection of stool specimens and repeat PCR for Rotaviruses/Noroviruses/Astroviruses/Adenoviruses, Shigella spp., EIEC, Salmonella spp., and Campylobacter spp. will be performed on Days 3, 4, and 6 of inpatient observation and after discharge from the hospital (Day 10); collection of blood and urine specimens for safety tests will be carried out at baseline and before hospital discharge (day 6). The recording of the intake of study therapies and of concomitant medications as well as the assessment of compliance with and safety of the study therapies will be performed on Days 2-6 and 10.

Patients who recovered while in hospital and are discharged from the unit earlier than at 5 days will undergo the procedures of Visit 6, including the collection of biological specimens for PCR (efficacy evaluation) and biochemistry, blood test and urinalysis (safety assessment). The parents/adopters will be given the blister pack with the remaining study drug so that the patient can continue the treatment.

Inclusion and exclusion criteria

Inclusion criteria

- 1. Patients of either gender aged from 6 months to 6 years old hospitalized to infectious department.
- 2. Diarrhea (watery stool without visible abnormal foreign substances [transparent mucus is possible] ≥ 3 times a day).
- 3. Dehydration symptoms according to CDS scale ≥ 1 .
- 4. The first 48 hours from the onset of the first diarrhea episode.
- 5. Start of study treatment (Ergoferon/Placebo) within 12 hours after the start of the standard hospital therapy.

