- 6. Availability of a patient information sheet (Informed Consent form) signed by the patient's parents/adopters to confirm the child's participation in the clinical trial signed by one parent/adopter of patient.

Exclusion criteria

1. Suspected bacterial intestinal infection.

CONFIDENTIAL Page 4 of 14

- 2. Suspected infectious diseases of another localization including pneumonia, meningitis, sepsis, otitis media, urinary tract infection, etc.
- 3. Severe intestinal infection⁷.
- 4. Severe dehydration (CDS score \geq 7).
- 5. Anuria (acute kidney injury).
- Medical history or prior diagnosis of serious diseases, including primary/secondary immunodeficieny, oncological disease, diabetes mellitus, infantile cerebral palsy, mucoviscidosis/cystic fibrosis etc.
- 7. Exacerbation or decompensation of a chronic disease, including diseases of the digestive system that would affect the patient's ability to participate in the clinical trial.
- 8. Malabsorption syndrome, including congenital or acquired lactose intolerance/lactase deficiency or any other disaccharidase deficiency and galactosemia.
- 9. Allergy/ intolerance to any of the components of study drugs.
- 10. Course administration of any medicines listed in the section "Prohibited concomitant treatment" for 2 weeks prior to the enrollment in the trial.
- 11. Participation in other clinical trials within 3 months prior to the enrollment in this study.
- 12. Patients whose parents/adopters, from investigator's point of view, will fail to comply with the observation requirements of the trial or with the dosing regimen of the study drugs.
- 13. The patient's parent/adoptive parent are a study specialist of the centre and is directly involved in the study, or is an immediate family member of the Investigator. Spouses, parents, children, or siblings, regardless of whether they are siblings or adopted are considered immediate family members.
- 14. The patient's parent/adoptive parent works for OOO "NPF "Materia Medica Holding", i.e. they are employees of the Company, temporary employees on a contract basis or appointed officials responsible for conduction of the study or their immediate family members.

Criteria for Withdrawal or Termination

- 1. The patient's inability or refusal of the patient or parents/adopters to follow the protocol requirements.
- 2. The necessity to use medications prohibited within this trial.
- 3. An adverse event requiring discontinuation of the study drug.

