- 4. The patient's or his/her parent/adopter wish to complete the study ahead of schedule for any reason.

CONFIDENTIAL Page 5 of 14

_

⁷ Criteria for a severe intestinal infection: sudden patient deterioration, sudden fatigue or even adynamia, marked apathy and drowsiness/excessive sleepiness and lethargy, dry mucous membranes, sunken eyes, loss of tearing, pool tissue turgor, lack of eye contact in the child on examination, aversion to food and drink, severe tachycardia/bradycardia, unstable hemodynamics, tachypnea, hypo- or hyperventilation, impaired microcirculation, peripheral cyanosis, slow capillary nail refill, persistent vomiting, anuria/acute renal disease, convulsions, and meningism.

- 5. Cases not specified by the protocol when, according to the investigator's opinion, further participation in the study harms the patient.
- 6. Incorrect inclusion of ineligible patient.
- 7. Early discharge of patient from hospital with persisting acute intestinal infection symptoms on days 2-5 of hospitalization, before the end of taking the study therapy at the parent's/adopter's request.

Number of subjects

It is planned to enroll 572 patients, which is expected to allow completion of all protocol procedures by at least 286 PCR-positive (for viral acute intestinal infection) patients (143 patients in the Ergoferon and Placebo groups).

Interim analysis

An interim statistical analysis will be performed as part of this study.

The interim analysis will be based on the patient assessment data and treatment outcomes recorded for the protocol-defined number of patients who have completed participation in the study.

Number of patients to be evaluated in the interim analysis:

144 patients (72 in the Ergoferon group and 72 in the Placebo group).

Number of patients to be evaluated in the final analysis:

286 patients (143 in the Ergoferon group and 143 in the Placebo group).

Treatment

Group 1

Name of the medicinal product: Ergoferon

Active ingredient: affinity purified antibodies to human gamma interferon -0.006 g*, affinity purified antibodies to histamine -0.006 g*, affinity purified antibodies to CD4 -0.006 g*

* Mixture of water-ethanol dilutions 100^{12} , 100^{30} , 100^{50} of active substance used for saturation of lactose monohydrate.

Excipients: Lactose monohydrate -0.267 g, microcrystalline cellulose -0.03 g, magnesium stearate -0.003 g.

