 - b. assumption on expected effects declared in the main efficacy criterion of the protocol.
- 1.8 calculation of sample size of groups 1 and 2 for two-sided test for interim and final analysis will be made using the formula:

$$N_1=N_2=(\sigma_1^2+\sigma_2^2)I$$

where N_1 and N_2 are sample sizes in Ergoferon and Placebo groups;

 σ_1 and σ_2 are expected standard deviations in groups 1 and 2;

I – Fisher's information determined using the formula:

$$I=(F^{-1}(1-\alpha)+F^{-1}(1-\beta))^2/\theta^2$$
,

CONFIDENTIAL Page 11 of 14

where $F^{-1}(1-\alpha)$ and $F^{-1}(1-\beta)$ are tabular values of z-test for α and β , a $\theta = (m_1-m_2)$.

1.9 final sample size will be determined using the formula:

$$N_F = N_{PP}/(1-C_w)$$
,

where N_F – final sample size;

N_{PP} – result of calculation in cl. 1.8, i.e. scheduled number of subjects completing the study per protocol;

 C_W – withdrawal coefficient.

2. Assumptions about the expected effects of the clinical study.

Given that the results of the previous studies, the difference between Ergoferon effect consisting in reduced mean diarrhea duration and Placebo effect is expected to be at least 12 hours in favour of Ergoferon with group standard deviation of at least 36 hours¹¹.

According to the statistical considerations and assumptions above, each group size will be:

- a) at interim analysis 72 subjects;
- b) at final analysis 143 subjects.

Hence, full PP analysis set will included 286 patients.

Given potential negative results of PCR diagnosis, screening failures and further withdrawals for various reasons it was decided to double the sample (C_w =50%) and and enroll at least 572 subjects (286 per group).

Statistical criteria

All the statistical calculations will be performed using two groups of statistical criteria:

- parametric to evaluate continuous and interval random variables;
- non-parametric for:
 - assessments of equality / inequality in the proportion of patients when compared for different visits,
 - analysis of frequencies of the compared features,
 - assessment of continuous and interval random variables in case of violation of the normality assumption.

The following SAS procedures are supposed to be used for interim analysis:

- SEQDESIGN, SEQTEST design and performance of interim analysis.
- Conditions for early study termination will be established using O'Brien-Fleming stopping boundary.

Parametric criteria

CONFIDENTIAL Page 12 of 14

11

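### The 50% loss allowance is fully used up by PCR-negative children, so 572 enrolled gives 286 virus-positive completers only if none of them is lost

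*Combined protocol and SAP*

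**What the plan says.** Three statements in the combined protocol and SAP bear on this.

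- **Footnote 6 (Study design)**, with the stated purpose of securing enough data for the efficacy analysis: "it is statistically assumed that 50% of patients will test negative for viral etiology of acute intestinal infection".
- **Evaluation of sample size, section 2:** "Given potential negative results of PCR diagnosis, screening failures and further withdrawals for various reasons it was decided to double the sample". The coefficient is C_w = 50%, and item 1.9 divides the per-protocol number by (1 − C_w), so 286 becomes 572.
- **Number of subjects:** 572 enrolled is "expected to allow completion of all protocol procedures by at least 286 PCR-positive (for viral acute intestinal infection) patients".

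No separate withdrawal rate appears anywhere, although the plan foresees losses after enrolment. Criteria for Withdrawal or Termination has seven items, among them "The necessity to use medications prohibited within this trial" and "Early discharge of patient from hospital with persisting acute intestinal infection symptoms on days 2-5 of hospitalization". The per-protocol set excludes children with a missed visit or a significant deviation. Footnote 6 also removes children with a bacterial finding: "patient whose PCR test indicates a bacterial etiology of acute intestinal infection will not be included in the analysis of treatment efficacy".

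**The concern.** One 50% allowance appears to be spent twice. Footnote 6 gives all of it to PCR-negative children, while the sample-size section says it also absorbs screening failures and withdrawals. Both can be true only if those other losses are zero among the virus-positive children.

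Because withdrawals are named as a loss the doubling covers, a reader will take 286 completers and 80% power at 572 as figures already net of withdrawal. On footnote 6 they are not. What is at stake is the expected number of virus-positive completers and the power of the primary comparison.

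**Working it through.** **Inputs from the documents.** Difference 12 h and SD 36 h per group (Evaluation of sample size, section 2); two-sided 5% and power 80% (items 1.1 to 1.3); O'Brien-Fleming boundary with looks at fractions 0.5 and 1.0 (item 1.6); 144 patients at the interim analysis and 286 at the final one; PCR-negative share 50% (footnote 6); enrolment 572.

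**Input not in the documents.** w, the share of enrolled virus-positive children who do not reach the per-protocol set. It is treated as an assumption and varied from 0 to 20%.

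**Step 1: reproduce the plan.**

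- Fixed design: n per group = 2 × 36² × (1.960 + 0.842)² / 12² = 141.3.
- The two-look O'Brien-Fleming critical values are 2.797 and 1.977. They inflate this by 1.0078 to 142.4, so 143 per group, with 71.2, so 72, at the interim.
- Enrolment: 286 / (1 − 0.50) = 572.

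All three stated figures (143, 72, 572) are recovered, so the sums themselves are right.

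**Step 2: apply footnote 6 to 572.** 572 × 0.50 = 286 virus-positive children before any other loss.

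**Step 3: add the other losses.** Losses among PCR-negative children cost nothing further, so only w matters:

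1 − C_w = (1 − 0.50)(1 − w)

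C_w = 50% holds only at w = 0. Expected virus-positive completers are 572 × 0.50 × (1 − w) = 286(1 − w).

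**Step 4: power.** With n completers per group, the standardised drift is 12 / (36√(2/n)). Power is the probability of crossing 2.797 at the interim or 1.977 at the end (normal approximation).

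| w | Actual C_w | Expected completers | Power | 144 as fraction of completers | Power at that fraction |
|---|---|---|---|---|---|
| 0 | 50% | 286 | 80.2% | 0.50 | 80.2% |
| 5% | 52.5% | 272 | 78.1% | 0.53 | 78.1% |
| 10% | 55% | 257 | 75.9% | 0.56 | 75.8% |
| 15% | 57.5% | 243 | 73.5% | 0.59 | 73.3% |
| 20% | 60% | 229 | 70.9% | 0.63 | 70.6% |

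The last column recomputes the boundary at the shifted interim fraction; this costs at most 0.3 points. On the same approximation, 285 completers give 80.03% and 284 give 79.9%, so there is essentially no slack. Power reaches 75% at 125.9 per group, a w of about 12%.

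**Step 5: sensitivity at w = 10%.** A 13 h difference gives 82%; an SD of 38 h gives 71%. The related-product study in footnote 11 reports a difference of 1.0 day (24 h) with SDs of 28.8 and 43.2 h, root mean square 36.7 h. If that held, power would exceed 99% even at w = 20%.

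**Step 6: the reverse question.** For 50% to be the combined loss, the PCR-negative share would have to be 1 − 0.5/(1 − w): 47.4% at w = 5%, 44.4% at 10%, 41.2% at 15% and 37.5% at 20%. Each is below the figure in footnote 6.

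**The case against.** The strongest reply is that 50% is a round, combined planning allowance. No sum is wrong, and uncertainty in the 50% is as large as the effect claimed. If the PCR-negative share were 45%, 572 × 0.55 would give about 315 virus-positive children and 83.8% power before other losses. This is fair as a statement about uncertainty, but footnote 6 assigns the whole 50% to PCR-negatives. If a combined allowance was meant, the footnote is what needs correcting.

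Other points, and what stands of them:

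- **Room to enrol more.** The sample-size section sets 572 as a minimum, and item 1.6 allows adjustment at the interim analysis. Either could still bring the trial to 286. But item 1.6 gives no adjustment rule, and neither provision is described as an allowance for withdrawals.
- **The size is not documented.** True: with no w stated, the power figures are conditional. A 5-day course with inpatient observation to Day 6 may keep w low. The contradiction itself needs no value of w.
- **The one-child margin is a rounding artefact.** Largely conceded. It comes from rounding 142.4 up to 143, and a simulated t-test gives about 80.0% at 143 per group. The point is only that there is no reserve.
- **The analysis sets do not expressly require PCR positivity.** Correct, and the documents do not say how a child positive for both a virus and a bacterium is classed. The finding concerns the 286 PCR-positive completers that Number of subjects describes, not the Full Analysis Set.
- **Screening failures.** These count only if 572 includes children screened out. Study design suggests it does not: "If inclusion criteria are met and non-inclusion criteria are absent (day 1), the patient will be included in the trial and randomized". They are left out of w here.

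**Conclusion.** The concern holds. Footnote 6, the C_w sentence and Number of subjects agree only at w = 0, and the plan names withdrawals as a loss that the doubling covers. For any w above zero, 572 is expected to give 286(1 − w) virus-positive completers. At w = 5% to 10% that means 14 to 29 fewer than stated and about 2 to 4 points less power; at 20% it means about 57 fewer and 9 points.

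These sizes rest on footnote 6's 50%, an assumed w, exactly 572 enrolled, and the planned 12 h difference with SD 36 h. An overall withdrawal rate must not be substituted for w. The effect is modest at small w, and type I error and the estimate are untouched. It should be fixed because the stated size and power are not what the plan's own assumptions deliver.

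**What to change.** Reconcile footnote 6, Number of subjects and Evaluation of sample size. State the PCR-negative share and w separately, say whether 572 is counted after screening, and define 1 − C_w = (1 − PCR-negative share)(1 − w). Then take one of two routes, according to what was meant.

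- **If 50% is the combined loss:** correct footnote 6 to a PCR-negative share of 1 − 0.5/(1 − w), for example 44.4% at w = 10%, provided the sponsor can support that share as an expectation. The figures 286, 572 and 80%, item 1.9 and the 0.5 interim fraction then agree. Cost: wording in footnote 6 and the C_w sentence.
- **If 50% PCR-negative is kept:** label 143 per group, 286 and 80% as the target, and state separately what 572 is expected to give, for example 257 completers and 76% power at w = 10%. Item 1.9 must then say that enrolment is held at 572 rather than derived from 286. Item 1.6b and the interim count must be brought into line, either by restating the fraction for 144 patients (0.56 at w = 10%) or by moving the count to keep 0.5. Cost: wording in the sample-size and interim sections, and a stated power a few points lower.

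Neither route adds patients or visits or changes the method.

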Method of administration: Tablet for oral use. Dose per administration - 1 tablet per intake (outside a meal/feeding). Within the first 2 hours - 1 tablet every 30 minutes, followed by 3 more tablets at time intervals equally separated throughout the rest of the day; from day 2 to day 5-1 tablet 3 times daily. For oral administration to a child aged from 6 months to 3 years old the

CONFIDENTIAL Page 6 of 14

tablet should be dissolved in 10 mL of boiled water of room temperature (or solution used for oral rehydration).

Dosage form: Tablets.

Description: White to off-white, round, flat, scored on one side and beveled tablets.

Storage conditions: Store in a place protected from light, at the temperature not exceeding 25°C. Keep out of the reach of children.

Group 2

Name of the medicinal product: Placebo

Active ingredient: NA

Excipients: Lactose monohydrate -0.267 g, microcrystalline cellulose -0.03 g, magnesium stearate -0.003 g.

Method of administration: Placebo using Ergoferon scheme.

Dosage form: Tablets.

Description: White to off-white, round, flat, scored on one side and beveled tablets.

Storage conditions: Store in a place protected from light, at the temperature not exceeding 25°C. Keep out of the reach of children.

Treatment duration

Ergoferon/Placebo treatment duration is 5 days.

Observation period

In total, the patient is observed up for 10 days (screening, randomization, treatment initiation – day 1, study therapy – days 1-5, hospital follow-up – day 6, personal visit (study site/home)/phone call – day 10).

Symptomatic (Standard) treatment

Throughout the study the patients can receive pathogenetic therapy for acute intestinal infections which includes:

1. Nutritional Interventions

Breast-feeding should not be interrupted. The volume and composition of food depends on the child's age, the severity of diarrhea symptoms, and preceding diseases. The frequency of feeding and amount of food per meal is determined by the child's age and presence and frequency of vomiting/regurgitation.

- 2) Oral rehydration using hypoosmotic rehydration compound Hydrovit ®⁸.
- 3) Intestinal adsorbent (diosmectite Smecta®).
- 4) Probiotic (Linex[®]).

CONFIDENTIAL Page 7 of 14

_

⁸ In medical centers of Uzbekistan the oral rehydration formulations authorized in these countries will be used.

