Medical history	+						
Physical examination	+	+	+	+	+	+	
Body weight measurement	+					+	
Body length/height measurement	+						
Evaluation of dehydration symptoms using CDS	+	+	+	+	+	+	
Diary supply	+						
Checking the correctness of filling the diary		+	+	+	+	+	
Parent/adopter inquiry (personal/by phone) and filling questionnaire "Parent's/adopter's inquiry data"							+
Return of patient diary						+	
Concomitant therapy	+	+	+	+	+	+	+
Eligibility assessment	+						
Obtaining stool sample for PCR diagnosis	+		+	+		+	+*
Safety laboratory tests (hematology, serum chemistry,	+					+	

CONFIDENTIAL Page 9 of 14

urinalysis)							
Randomization and prescription of study drug	+						
Study drug supply							
, , , , , , , , , , , , , , , , , , ,	T .						
Basic medication supply	+	+	+	+	+		
Study drug accountability,						+ **	+ **
compliance assessment						Į.	!
Evaluation of treatment safety	+	+	+	+	+	+	+

^{*} All the subjects will receive sterile containers for stool storage and transportation on day 10. In case of a phone visit on day 10 stool samples will be delivered to the local laboratory by a courier.

Statistical Analyses.

Samples

Total set: all patients included in the study whose parents/adoptive parents signed the Informed Consent Form for the patient's participation in the study. All AEs including those occurred prior to the study therapy will be considered throughout the study for this sample.

Safety population: all patients who received at least one dose of the study drug. This sample will be used to *analyze the study treatment safety and tolerability*, since all the AEs identified after the study product administration will be recorded.

Full Analysis Set. This sample includes all enrolled and randomized patients, except for those who have experienced at least one of the following events:

- 1) non-compliance with inclusion / exclusion criteria;
- 2) the patient has not taken a single dose of the study drug;
- 3) lack of any data of the patient following randomization;
- 4) withdrawal of a patient due to early discharge (discharge of patient with persistent symptoms of acute intestinal infections on days 2-5 of hospitalization before the study treatment is completed at the parent's/adopter's request).

This sample is the most consistent with the "Intention-to-treat" principle, will be used for the *Intention-to-treat analysis (ITT analysis) of the the study therapy efficacy*.

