Per protocol set. This sample includes all patients who completed the therapy as per the study protocol without any missing visits or significant protocol deviations. This sample will be used for the *Per Protocol analysis (PP- analysis) of the the study therapy efficacy*.

Mean value in Placebo group for the relevant day will be used to fill lacking/missing data.

Data treatment and all statistical calculations under the protocol will be made using SAS-9.4 statistical software¹⁰.

CONFIDENTIAL Page 10 of 14

^{**} Return of the study product is made after 5-day treatment course (on Day 6). If the subject is discharged sooner than on day 6, the parent/adopter will be given a blister with the remaining product to complete outpatient therapy; in this case the product return and determination of compliance will be made on Day 10 ± 1 .

¹⁰ Holder of license: OOO "NPF "Materia Medica Holding", No. 70100045.

Evaluation of sample size

The sample size has been assessed on the basis of the following rules and assumptions:

- 1. Statistical provisions.
 - 1.1 the power of the statistical tests " $P = (1 \beta)$ " is assumed to be 80% (the probability of correct rejection of the null hypothesis is 0.8);
 - 1.2 the probability of a type I error " α " is allowed to be less than 5% (the probability of the erroneous acceptance of an alternative hypothesis is less than 0.05);
 - 1.3 the statistical criteria are 2-sided;
 - 1.4 the calculation of the sample size is based on the assumptions about the expected effects, mainly declared in the primary efficacy criterion of the Protocol;
 - 1.5 statistical null and alternative hypotheses are formulated as follows:

$$H_0: m_2-m_1 \le 0$$

$$H_1: m_2-m_1>0,$$

where $\mathbf{m_1}$ – mean disease duration in Ergoferon group,

m₂ – mean disease duration in Placebo group;

- 1.6 to assure potential adjustment of sample size or terminate the study due to inadequate efficacy/high efficacy, interim analysis will be carried out in which:
 - a. calculations will be made using O'Brien-Fleming boundary;
 - b. proportions of the subjects completing the study and yielding the results for interim and final analyses, will be taken as 0.5 and 1.0 (i.e. interim analysis will be made after recruitment of half of the planned number of the clinical study subjects.
- 1.7 therefore, sample size will be calculated taking into account
 - a. interim analysis;

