¹¹ According to the report for multicenter double-blind placebo-controlled parallel-group randomized clinical study of therapeutic efficacy and safety of anti-IFN at rotavirus infection in children (phase III), mean diarrhea duration in active product group was 1.9±1.2 days, in Placebo group - 2.9±1.8 days.

The application of parametric criteria will be accompanied by a check for normality of the compared samples (Kolmogorov-Smirnov test).

The following parametric methods and approaches are supposed to be used:

- 1. To assess the differences of continuous variables obtained in two different (independent) groups –Student t-test for independent samples.
- To assess the differences of continuous variables obtained in one group at two different visits – Student t-test for for paired samples.
- 3. To assess the temporal dynamics of the compared indicators analysis of variance (ANOVA) or covariance (ANCOVA) in the modification with repeated measures.
- 4. In case of multiple comparisons between the groups will apply a variety of corrections for multiplicity Dunnett, Tukey, Scheffe, Holm adaptive test, etc.
- 5. In case of abnormal data distribution, approaches with the Generalized Linear Models and / or Mixed Linear Models will be used.
- 6. Selection of the type of distribution, clarification of the factor and covariance structures of the model is carried out with fit statistics such as AIC (Akaike information criterion).

To perform the above-mentioned statistical tests and techniques, it is assumed that the following SAS procedures are used:

- UNIVARIATE check for normality of the compared distributions;
- CORR, MEANS calculation of descriptive statistics;
- TTEST Student t-test with all the modifications;
- GLM analysis of Generalized Linear Models for studying temporal dynamics (ANOVA, ANCOVA);
- GENMOD analysis of Generalized Linear Models.
 MIXED analysis of Generalized Linear Models.

Non-parametric criteria

Below, there are the main types of possible comparisons with the respective criteria:

- 1. To assess the differences of continuous variables obtained in two different (independent) groups Mann-Whitney U-test.
- 2. To assess the temporal dynamics of the compared indicators Friedman test, non-parametric analogue of analysis of variance with repeated measures.

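### No covariate is prespecified for the primary endpoint, and the default test is unadjusted; naming an ANCOVA with a few baseline covariates would be a cheap efficiency gain

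*Combined protocol and SAP*

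**What the plan says.** The primary endpoint is average diarrhea duration, counted from the first dose of study drug (Endpoints, footnote 1).

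No test is assigned to it by name. The section on statistical criteria gives a menu:

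- Parametric criteria, item 1: for continuous variables in two independent groups, "Student t-test for independent samples".
- Non-parametric criteria, item 1: Mann-Whitney for the same comparison.
- Parametric criteria, item 3: ANOVA or ANCOVA, in repeated-measures form, for change over time.
- Parametric criteria, items 5 and 6: generalized linear or mixed models when the data are not normal, with distribution, factors and covariance structure guided by fit statistics such as AIC.

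No covariate is named for any of these.

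The sample size section plans on an effect that "is expected to be at least 12 hours in favour of Ergoferon with group standard deviation of at least 36 hours". It states that "the statistical criteria are 2-sided", and its formula has no term for covariates.

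On baseline data, the Schedule of study procedures has "Evaluation of dehydration symptoms using CDS" on Day 1. Inclusion criterion 4 is "The first 48 hours from the onset of the first diarrhea episode". Age from 6 months to 6 years is inclusion criterion 1. Inclusion criterion 3 and exclusion criterion 4 together limit CDS at entry to at least 1 and below 7. Footnote 8 says: "In medical centers of Uzbekistan the oral rehydration formulations authorized in these countries will be used".

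**The concern.** Children can enter at any time in the first 48 hours of illness, yet the endpoint clock starts only at first dose. A child enrolled late may have less diarrhea left to run than one enrolled early. Baseline dehydration, age and country (through local rehydration products) are also plausible predictors of the remaining duration. An unadjusted comparison leaves whatever these variables explain in the error term. The confidence interval on the primary endpoint is then wider, and power lower, than the same patients could give.

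There is a second, smaller issue. The plan lets a model be built under non-normality but fixes no covariates, so any adjustment that did occur could be chosen after the data are seen.

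**Working it through.** **Inputs from the sample size section.** Type I error "is allowed to be less than 5" percent, two-sided; power "is assumed to be 80" percent; difference 12 h; SD 36 h in each group; O'Brien-Fleming boundary with looks at information fractions 0.5 and 1.0; 143 per group at the final analysis and 72 at the interim.

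**Step 1: reproduce the plan's figure.** The plan's formula is n per group = (36² + 36²) × θ² / 12² = 18 × θ², where θ is the required drift.

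- Fixed design, two-sided 5%: θ² = (1.960 + 0.842)² = 7.849, so n = 141.28, rounded up to 142.
- Two-look O'Brien-Fleming: critical z 2.797 and 1.977, θ = 2.8125, inflation 1.0078. So n = 142.38, rounded up to 143, with 71.19, rounded up to 72, at the interim.

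Both match the plan. A one-sided 5% version gives 113.02 and does not match. Then 286 / (1 − 0.5) = 572, which also matches. The plan is therefore sized for an unadjusted comparison on the raw 36 h SD, and power at 143 per group is 80.2%.

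**Step 2: effect of adjustment.** With covariates explaining a share R² of the variance, the residual SD is 36 × √(1 − R²) and the drift is 12 / (36 × √(1 − R²) × √(2/143)) = 2.819 / √(1 − R²). The documents give no R², so the first column is an assumption.

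| R² (assumed) | Residual SD (h) | Power at 143 per group, O'Brien-Fleming | n per group for 80% |
|---|---|---|---|
| 0 | 36.0 | 80.2% | 143 |
| 0.05 | 35.1 | 82.1% | 136 |
| 0.10 | 34.2 | 84.1% | 129 |
| 0.20 | 32.2 | 88.1% | 114 |
| 0.30 | 30.1 | 91.9% | 100 |

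**Step 3: cost of the covariate parameters.** The table ignores this cost. For k parameters, use a t-test with 286 − 2 − k degrees of freedom and a variance inflated by 1 + k/(286 − k − 3), in a fixed design for simplicity.

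- k = 4: inflation 1 + 4/279 = 1.0143. Power at R² = 0 falls from 80.2% to 79.7%, about 0.6 points before rounding (80.21 to 79.65).
- k = 8: inflation 1 + 8/275 = 1.0291. Power at R² = 0 falls to 79.1%, about 1.1 points (80.21 to 79.07).
- Break-even R² = 1 − 1/inflation, which is about 1.4% for k = 4 and 2.8% for k = 8.
- With k = 4, power net of this cost is 81.6, 83.6, 87.7 and 91.5% at R² of 5, 10, 20 and 30%.

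**Step 4: illustration for onset time alone.** Assume entry times uniform over 0 to 48 h, so SD = 48/√12 = 13.9 h. If each hour already ill shortens the remaining diarrhea by one hour, R² = (13.9/36)² = 15%. If it shortens it by half an hour, R² = (6.9/36)² = about 4%. Both exceed break-even. Neither the uniform spread nor the slopes come from the documents.

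**The case against.** The strongest reply is that nothing is broken. Under randomization the unadjusted comparison is valid, and Step 1 shows that it has the planned power on the plan's own assumptions. That stands in full.

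Several stronger readings are tempting, and the documents do not support them:

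- **That the t-test is the designated primary test.** It is the default entry in a conditional menu. The prior-study figures in footnote 11 (1.9 ± 1.2 and 2.9 ± 1.8 days) have SDs above 60% of the mean, which suggests skew, so Mann-Whitney or a model might be used instead. None of these routes has a named covariate, so the point survives. The document also calls itself a protocol summary, so its silence is weaker evidence about any fuller plan.
- **That adjustment costs nothing.** Step 3 shows a small loss if the covariates are uninformative.
- **That a gain of a given size is assured.** No R² is given, and the entry limits on CDS and onset time narrow their range, which may lower it.
- **That chance imbalance in onset time biases the estimate.** It does not; the unadjusted standard error already allows for it. Adjustment removes that part of the noise.
- **That all four covariates are listed as collected.** Only CDS is explicit on Day 1. Age and onset time must be established for eligibility, and country follows from site. Onset might be recorded only as a yes/no check.
- **That a Cox model would serve equally well.** The hypotheses in item 1.5 are about a difference in means. A Cox model estimates a hazard ratio, and the calculation in Step 2 does not apply to it.

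**Conclusion.** The point holds as a missed efficiency, with no error in the default test or in the sample size. At 143 per group, adjustment would add about 2 power points at R² = 5%, 4 at 10%, 8 at 20% and 12 at 30%, against a loss of about 0.6 to 1.1 points if the covariates explain nothing. These figures rest on the plan's 12 h difference and 36 h SD and on an assumed R². What is firm is the asymmetry: the covariates need to explain only about 1.4 to 2.8% of the variance to pay for themselves. Fixing the list in advance also closes off covariate selection by AIC after the data are seen. This is a cheap improvement that is worth making.

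**What to change.** - Name one primary analysis: an ANCOVA for the difference in mean diarrhea duration, with treatment plus baseline CDS, hours from first diarrhea episode to first dose, age, and country. Offer no Cox alternative.
- Fix the form of each covariate, the coding of country and the handling of missing covariate values before unblinding, and exempt this model from AIC-based selection.
- Use the same adjusted statistic at the interim and final O'Brien-Fleming looks.
- Keep 143 per group, so that any gain becomes extra power, and report the unadjusted test as supportive.
- Confirm that the time of the first diarrhea episode is recorded as a value and not only as an eligibility tick.

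The cost is a short paragraph in the SAP, possibly one data field for onset time, and the small loss of power shown above if the covariates prove uninformative. No additional patients or visits are needed.
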